## REVISION HISTORY

Revision #	Version Date	Summary of Changes	Consent Change?
1.1	July 15, 2020	Revisions made in response to comments from the CCRC review (prior to DHH IRB review).	N/A
1.2	July 28, 2020	Revisions made in response to 7/27/20 comments from CCRC review	N/A
2.0	Aug. 20, 2020	Revised to include plan to collect DHH billing data for participants.	N/A
3.0	June 15, 2021	Revisions to protocol to include clarification of eligibility criteria and dosing algorithm	N/A
4.0	September 30, 2022	Revision to increase accrual goal from 50 to 53 patients, to allow for a greater-than-anticipated number of inevaluable patients.	N/A

PROTOCOL TITLE: A pragmatic, single-arm clinical trial of a novel dose adjustment algorithm for preventing cytopenia-related delays during FOLFOX chemotherapy

## 1.0 Study Summary

Study Title	A pragmatic, single-arm clinical trial of a novel dose adjustment algorithm for preventing cytopenia-related delays during FOLFOX chemotherapy
Study Design	Single-arm clinical trial (single-stage phase II design)
Primary Objective	To evaluate the effectiveness of an adaptive chemotherapy dose adjustment algorithm for reducing unplanned delays during cycles 2-6 of FOLFOX chemotherapy
Secondary Objective(s)	
 
• To confirm the safety of the FOLFOX dose adjustment algorithm
 
• To evaluate the relative dose intensity of FOLFOX chemotherapy in patients managed according to the investigational dose adjustment algorithm
 
• To estimate out-of-pocket costs associated with chemotherapy treatment visits and unplanned chemotherapy delays
 

Research Intervention(s)/ Investigational Agent(s)	Implementation of an investigator-developed chemotherapy dose adjustment algorithm to guide chemotherapy dose reductions and delays related to neutropenia or thrombocytopenia
IND/IDE #	Not applicable
Study Population	Adult patients with gastrointestinal cancer receiving first-line chemotherapy with FOLFOX-type regimens at the Norris Cotton Cancer Center
Sample Size	53 patients (45 evaluable patients)
Study Duration for individual participants	Approximately 12 weeks
Study Specific Abbreviations/ Definitions	
FOLFOX: 5-fluorouracil, folinic acid, and oxaliplatin      ANC: Absolute neutrophil count      RDI: Relative dose intensity

PROTOCOL TITLE: A pragmatic, single-arm clinical trial of a novel dose adjustment algorithm for preventing cytopenia-related delays during FOLFOX chemotherapy

## 2.0 Objectives\*

- We will test an intervention of an investigator-developed chemotherapy dose adjustment algorithm, with the long-term goal of reducing unplanned cytopenia-related treatment delays during FOLFOX chemotherapy.
- The primary objective of this study is to evaluate the effectiveness of the investigator-developed chemotherapy dose adjustment algorithm for reducing unplanned delays in patients receiving FOLFOX-type chemotherapy. In a historical cohort, 40% of patients experienced at least one delay in cycles 2-6 of FOLFOX chemotherapy. If the study intervention is successful, this proportion should be 20% or less.
- The secondary objectives of this study are:
  - To confirm the safety of the investigator-developed dose adjustment algorithm, by demonstrating that study algorithm is associated with a low rate of cytopenia-related adverse events.
  - To evaluate the dose intensity of FOLFOX chemotherapy in patients managed according to the investigational dose adjustment algorithm, relative to the standard dose intensity (RDI).
  - To estimate out-of-pocket costs associated with chemotherapy treatment visits and unplanned chemotherapy delays

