## 3.0 Background\*

Unplanned chemotherapy delays are a common and disruptive event during cancer treatment. Unplanned delays are disruptive for patients and their caregivers because they can lead to additional travel, clinic visits, blood draws, copays, and time away from home and work. Unplanned delays are also costly and inefficient for the health care delivery system, resulting in unused capacity at the time of the delay in addition to duplicative future clinic visits and laboratory testing. The most frequent cause of unplanned delays are cytopenias—reduced counts of white blood cells and/or platelets.

The modified FOLFOX (mFOLFOX) chemotherapy regimen is a key component of treatment for colorectal and gastroesophageal cancers, and unplanned delays due to cytopenias are common among patients receiving this regimen. In a retrospective, multi-site analysis of 214 patients with colorectal cancer—including over 100 patients from the Dartmouth Cancer Center (DCC)—we found that 43% of patients experienced one or more unplanned delays during the first six cycles of treatment. The majority of these delays were attributed to asymptomatic neutropenia or thrombocytopenia. eDH reporting shows that over 100 patients are treated with the mFOLFOX regimen each year at NCCC (Lebanon campus), highlighting the relevance of developing patient-centered approaches to prevent cytopenia-related treatment delays while maintaining the effectiveness of cancer treatment.

**PROTOCOL TITLE:** A pragmatic, single-arm clinical trial of a novel dose adjustment algorithm for preventing cytopenia-related delays during FOLFOX chemotherapy

The justification for delaying chemotherapy treatment in the face of reduced blood counts is to reduce risk for infection or bleeding. Clinical trial protocols have historically mandated both a one-week treatment delay and a chemotherapy dose-reduction for patients with grade  $\geq 3$  neutropenia (absolute neutrophil count  $< 1000/\text{mm}^3$ ) or grade  $\geq 2$  thrombocytopenia (platelet count  $< 75,000/\text{mm}^3$ ). This approach has been widely adopted in clinical practice; however, with nearly two decades of experience with the mFOLFOX regimen it is increasingly apparent that this reactive “delay and dose-reduce” approach is highly conservative and is associated with very low rates of fever and neutropenia (generally  $< 5\%$ ).

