## 5.0 Study Intervention/Investigational Agent

The study intervention will involve implementation of a clinical algorithm to guide chemotherapy dose reductions and treatment delays in patients with neutropenia and/or thrombocytopenia during treatment with FOLFOX-type regimens. The clinical algorithm (see **Appendix A**) was developed by the principal investigator, [name], based on clinical experience and published evidence regarding the safety of mFOLFOX administration in the setting of neutropenia and thrombocytopenia. [name] and colleagues have previously implemented many of the algorithm's features at DCC in the course of routine care, and [name] has iteratively revised the algorithm over time based on experiences from clinical use.

Features of the dose adjustment algorithm that differ from criteria used in clinical trial protocols and routine care include:

- At presentation for cycle 2 and 3 – the algorithm employs proactive chemotherapy dose reductions, without treatment delay, in patients with mild cytopenias (ANC 1000-1499/mm^3 and/or platelet count 75,000-99,000/mm^3).
  - *In usual care, mild cytopenias during early treatment cycles do not trigger a chemotherapy dose reduction, but these early cytopenia events often lead to more severe cytopenias and subsequent delays in later treatment cycles.*

PROTOCOL TITLE: A pragmatic, single-arm clinical trial of a novel dose adjustment algorithm for preventing cytopenia-related delays during FOLFOX chemotherapy

- At any cycle – the algorithm employs chemotherapy dose reductions without treatment delay in patients with moderate cytopenias (ANC 750-999/mm^3 and/or platelet count 50,000-74,000/mm^3).
  - *In usual care, moderate cytopenias trigger both a chemotherapy treatment delay AND a subsequent dose reduction, whereas the study algorithm will introduce a dose reduction without a treatment delay.*

Participating clinicians will be educated regarding the rationale and evidence support for the clinical algorithm as part of study initiation. Decisions about dose modifications and delays for reasons other than neutropenia and/or thrombocytopenia will be made at the discretion of the treating clinician, as per standard-of-care treatment.

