## 17.0 Data Management\* and Confidentiality

### *Data analysis plan*

The **primary analysis** will consist of evaluation of the proportion of study patients experiencing one or more unplanned treatment delays prior to cycle 6 of chemotherapy. Exact methods for binomial data will be used to provide 95% confidence intervals. A chi-squared test will be performed to compare this proportion to the estimate of 40% found in a historical cohort of patients from DCC and the University of Colorado.

The study will enroll a total of 50 participants in order to accrue 45 evaluable participants (accounting for a drop-out rate of 10%). This sample size of 45 participants provides power of 0.90 to detect a proportion of 20% or lower than the historical control of 40%, based on an exact chi-squared test with a one-sided significance level of 0.05.

Analyses of secondary endpoints will include reporting of the incidence of the events making up the composite safety outcome, calculation of the RDI (relative dose intensity, as previously defined in section 4.0) of mFOLFOX chemotherapy, and reporting of survey findings regarding patient out-of-pocket costs related to chemotherapy treatment visits (as a surrogate for out-of-pocket costs associated with cytopenia-related chemotherapy delays).

We will calculate RDI for each of the individual component drugs of the mFOLFOX regimen (oxaliplatin, 5-FU bolus, and 5-FU 46-hour infusion). We will report values of the mean, standard deviation, and 95% confidence intervals for the RDI of each drug. Bootstrap 95% confidence intervals for each RDI (*Statistical Science* 1996, Vol. 11, No. 3, 189–228) will be performed using the *boot* package in R.

We will report descriptive findings from the survey of patient out-of-pocket costs associated with chemotherapy treatment visits. Descriptive information will include patient-reported estimates of mean patient out-of-pocket costs for chemotherapy treatment visits related to travel, copayments, lost income, and child care, elder care, or pet care.

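### The safety analysis does not count or analyse patients dosed at moderate cytopenia, so a low overall event rate says little about the step that departs most from usual care

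*Combined protocol and SAP*

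**What the plan says.** The secondary safety objective in Section 2.0 is to be met "by demonstrating that study algorithm is associated with a low rate of cytopenia-related adverse events". No threshold, comparator or denominator is attached to it.

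The data analysis plan in Section 17.0 provides for "reporting of the incidence of the events making up the composite safety outcome". It defines no subset, no analysis by cycle and no interval for these events. That the incidence is taken over all patients is an inference, though a natural one.

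Section 5.0 names two departures from usual care:

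- At cycles 2 and 3, "the algorithm employs proactive chemotherapy dose reductions, without treatment delay, in patients with mild cytopenias". This gives less drug than usual care.
- At any cycle, "the algorithm employs chemotherapy dose reductions without treatment delay in patients with moderate cytopenias", meaning ANC 750-999 and/or platelets 50,000-74,000. The same section contrasts this with current practice: "In usual care, moderate cytopenias trigger both a chemotherapy treatment delay AND a subsequent dose reduction".

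Appendix A adds a second route to dosing at those counts. Patients held for ANC below 750 or platelets below 50,000 may restart once ANC is at least 750 and platelets exceed 50,000. Section 3.0 puts the customary delay thresholds at ANC below 1000 and platelets below 75,000.

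Section 18.0 stops the study if more than 3 patients have any component of the safety endpoint. It also considers whether each event is attributable to the algorithm, but no planned analysis uses that attribution.

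**The concern.** Section 3.0 explains that chemotherapy is delayed at low counts to limit infection and bleeding, and Section 15.0 concedes a theoretical added risk of symptomatic cytopenia. That risk bears mainly on doses given at counts where usual care would wait. Baseline neutropenia and thrombocytopenia are exclusions, so enrolment is not enriched for patients who will reach those counts.

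If only a minority reach them, the overall rate averages their risk with that of patients who never received such a dose. The trial could then declare safety confirmed without a reader being able to tell how many patients received the step in question or what happened to them afterwards.

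**Working it through.** **Inputs.** There are 45 evaluable patients (Section 17.0). The historical share with at least one delay is 40% in cycles 2-6 (Section 2.0); Section 3.0 gives 43% over the first six cycles. On cause, Section 3.0 says: "The majority of these delays were attributed to asymptomatic neutropenia or thrombocytopenia". The stopping rule is more than 3 patients (Section 18.0). The exposed share and the event risks are not in the documents and are assumed below.

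**1. The plan's own figure.** An exact one-sample binomial test with n = 45, rejecting when 12 or fewer patients are delayed, has size 0.0446 at 40% and power 0.9005 at 20%. The stated 0.90 is reproduced. It concerns the delay endpoint; no such figure exists for safety.

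**2. Exposed patients, assumed.** If 50% to 100% of delayed patients had a cytopenia-related delay, then 45 × 0.40 × 0.5 = 9 and 45 × 0.40 × 1.0 = 18.

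**3. What zero events would show.** The one-sided 95% upper bound is 1 − 0.05^(1/m). The upper limit of the exact two-sided 95% interval is 1 − 0.025^(1/m).

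| Denominator m | One-sided bound | Two-sided upper limit |
|---|---|---|
| 45 (all) | 6.4% | 7.9% |
| 18 (exposed, high) | 15.3% | 18.5% |
| 9 (exposed, low) | 28.3% | 33.6% |

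**4. Dilution.** Overall rate = f × p(exposed) + (1 − f) × p(unexposed). For illustration, take risks of 20% and 2%:

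- f = 20%: 0.20 × 0.20 + 0.80 × 0.02 = 5.6%
- f = 40%: 0.40 × 0.20 + 0.60 × 0.02 = 9.2%

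A tenfold difference in risk would thus appear as a single-digit overall rate.

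**5. The stopping rule.** A 45-patient trial that finishes without crossing it has at most 3 patients with events: 3/45 = 6.7%. If all three were exposed, the exposed rate would be 3/18 = 17% (exact 95% interval 3.6% to 41.4%) or 3/9 = 33% (7.5% to 70.1%). Under the risks in step 4, the chance of more than 3 patients with events is 24% at f = 20% (9 exposed) and 61% at f = 40% (18 exposed).

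**6. Which events can be linked to such a dose.** Section 9.0 ends monitoring at day 1 of cycle 6, so the interval after a dose is observed for cycles 2-5 only. A severe cytopenia found at planned day 1 of cycle 2 follows standard cycle 1 dosing, before the algorithm acts, yet could count in the composite. The overall rate can therefore also be pushed upward by events unrelated to the algorithm.

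**The case against.** The strongest reply is that the intervention is the whole algorithm. It is applied to every patient, and the early reductions may change who reaches moderate cytopenia. A centre adopting it needs the overall rate. This stands: the all-patient incidence is a legitimate result and should not be displaced.

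The stopping rule is a count, so unexposed patients do not dilute it, and attribution is considered event by event. This also stands as a safeguard. It still does not yield a rate for the exposed, and step 5 shows that the rule can often go uncrossed when the exposed risk is high.

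Four stronger readings are tempting, and the documents do not support them:

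- *The added risk lies only in on-time doses.* Appendix A restarts held patients at the same lowered counts. The near-total bar on G-CSF applies to everyone, and its effect cannot be judged because usual-care G-CSF use is not given.
- *The safety conclusion should rest on the exposed group alone.* That group is small and is selected by a low count after baseline. Comparing it with doses at higher counts would be confounded, since these patients already start nearer to grade 4. The trial has no delayed patients with the same counts to compare.
- *The number of on-time doses equals the delays avoided.* It misses delays prevented by the early reductions, includes delays merely postponed to a later cycle, and assumes that usual care would always have exceeded 18 days.
- *Most patients are certainly unexposed, with 18 as a ceiling.* Section 3.0 speaks of a majority of delays, not of delayed patients. Section 5.0 says many of the algorithm's features were already in local routine use, so patients treated through low counts would not appear as delays.

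**Conclusion.** The point holds as a gap in reporting and inference, not as an error in the all-patient rate. As planned, the trial can report a low rate without showing how many patients were dosed at ANC 750-999 and/or platelets 50,000-74,000, or how they fared. If 9 to 18 of 45 are exposed, an event-free trial bounds the overall risk at 6.4% but the risk in exposed patients only at about 15% to 28% (one-sided 95%).

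Those figures rest on the assumption that 50-100% of a 40% delay rate approximates exposure; the true share could lie outside that range. The 20% and 2% risks are illustrative only. The qualitative conclusion needs only that exposed patients be a modest part of the sample. The change should be made: it costs little and limits what the trial may claim about safety.

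**What to change.** In Section 17.0, keep the all-patient incidence as the measure of the whole strategy and add one table giving:

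- (a) the number of patients and of cycles dosed at ANC 750-999 and/or platelets 50,000-74,000, with on-time and post-hold doses shown separately;
- (b) the composite safety events between each such dose and the next planned day 1, for doses in cycles 2-5, with exact 95% intervals per exposed patient;
- (c) separately, any events found at or before planned day 1 of cycle 2.

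State in the plan that (b) is descriptive, without a causal comparison with doses at higher counts, and that (a) is not a count of delays avoided. Word the safety conclusion from both the overall and the exposed rates, and note the limited precision of the latter.

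The cost is one table. Section 6.0 already collects doses, dates, planned-day counts and the specified events for cycles 1-6; confirm that the count on the day of a restart is captured as well. The downside is a wide interval and a less favourable safety statement.

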## 3.0 Background\*

Unplanned chemotherapy delays are a common and disruptive event during cancer treatment. Unplanned delays are disruptive for patients and their caregivers because they can lead to additional travel, clinic visits, blood draws, copays, and time away from home and work. Unplanned delays are also costly and inefficient for the health care delivery system, resulting in unused capacity at the time of the delay in addition to duplicative future clinic visits and laboratory testing. The most frequent cause of unplanned delays are cytopenias—reduced counts of white blood cells and/or platelets.

The modified FOLFOX (mFOLFOX) chemotherapy regimen is a key component of treatment for colorectal and gastroesophageal cancers, and unplanned delays due to cytopenias are common among patients receiving this regimen. In a retrospective, multi-site analysis of 214 patients with colorectal cancer—including over 100 patients from the Dartmouth Cancer Center (DCC)—we found that 43% of patients experienced one or more unplanned delays during the first six cycles of treatment. The majority of these delays were attributed to asymptomatic neutropenia or thrombocytopenia. eDH reporting shows that over 100 patients are treated with the mFOLFOX regimen each year at NCCC (Lebanon campus), highlighting the relevance of developing patient-centered approaches to prevent cytopenia-related treatment delays while maintaining the effectiveness of cancer treatment.

**PROTOCOL TITLE:** A pragmatic, single-arm clinical trial of a novel dose adjustment algorithm for preventing cytopenia-related delays during FOLFOX chemotherapy

The justification for delaying chemotherapy treatment in the face of reduced blood counts is to reduce risk for infection or bleeding. Clinical trial protocols have historically mandated both a one-week treatment delay and a chemotherapy dose-reduction for patients with grade  $\geq 3$  neutropenia (absolute neutrophil count  $< 1000/\text{mm}^3$ ) or grade  $\geq 2$  thrombocytopenia (platelet count  $< 75,000/\text{mm}^3$ ). This approach has been widely adopted in clinical practice; however, with nearly two decades of experience with the mFOLFOX regimen it is increasingly apparent that this reactive “delay and dose-reduce” approach is highly conservative and is associated with very low rates of fever and neutropenia (generally  $< 5\%$ ).

In order to maximize benefits (e.g. cure in the adjuvant treatment setting, and prolonged survival in the palliative setting) and minimize harms of chemotherapy, new approaches are needed for more adaptive, individualized chemotherapy dose adjustment. We propose to test a strategic care delivery intervention—a chemotherapy dose adjustment algorithm—with the primary objective of demonstrating that the dose adjustment algorithm leads to a reduction in the proportion of patients with one or more delays prior to the completion of cycle 6 of mFOLFOX chemotherapy. The long-term research objective is to use the dose adjustment algorithm to safely increase on-time delivery of mFOLFOX chemotherapy in real-world clinical practice, reducing cytopenia-related treatment delays and the attendant burdens and costs while maintaining treatment effectiveness.

## 5.0 Study Intervention/Investigational Agent

The study intervention will involve implementation of a clinical algorithm to guide chemotherapy dose reductions and treatment delays in patients with neutropenia and/or thrombocytopenia during treatment with FOLFOX-type regimens. The clinical algorithm (see **Appendix A**) was developed by the principal investigator, [name], based on clinical experience and published evidence regarding the safety of mFOLFOX administration in the setting of neutropenia and thrombocytopenia. [name] and colleagues have previously implemented many of the algorithm's features at DCC in the course of routine care, and [name] has iteratively revised the algorithm over time based on experiences from clinical use.

Features of the dose adjustment algorithm that differ from criteria used in clinical trial protocols and routine care include:

- At presentation for cycle 2 and 3 – the algorithm employs proactive chemotherapy dose reductions, without treatment delay, in patients with mild cytopenias (ANC 1000-1499/mm^3 and/or platelet count 75,000-99,000/mm^3).
  - *In usual care, mild cytopenias during early treatment cycles do not trigger a chemotherapy dose reduction, but these early cytopenia events often lead to more severe cytopenias and subsequent delays in later treatment cycles.*

PROTOCOL TITLE: A pragmatic, single-arm clinical trial of a novel dose adjustment algorithm for preventing cytopenia-related delays during FOLFOX chemotherapy

- At any cycle – the algorithm employs chemotherapy dose reductions without treatment delay in patients with moderate cytopenias (ANC 750-999/mm^3 and/or platelet count 50,000-74,000/mm^3).
  - *In usual care, moderate cytopenias trigger both a chemotherapy treatment delay AND a subsequent dose reduction, whereas the study algorithm will introduce a dose reduction without a treatment delay.*

Participating clinicians will be educated regarding the rationale and evidence support for the clinical algorithm as part of study initiation. Decisions about dose modifications and delays for reasons other than neutropenia and/or thrombocytopenia will be made at the discretion of the treating clinician, as per standard-of-care treatment.

